5.4.1.1.5. Functional Cure

Functional cure will be evaluated at each of the following time points separately: FU Week 12, 24, 36 and 48. A participant will be defined as having achieved functional cure (FC) if he/she has:

- met the criteria for stopping NA treatment at Week 24, and
- had HBsAg seroclearance at the given week of interest, and
- not required NA re-treatment between FU Week 2 and the given week of interest.

It can be noted that a participant may achieve HBsAg seroclearance prior to the week of interest, but the HBsAg level <LLOQ has to be shown at the given week of interest to be counted as responder.

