5.4.1.1.4. HBsAg Seroclearance

Seroclearance of HBsAg is defined as a (quantitative) HBsAg level <LLOQ (see [Table 5](#)). HBsAg seroclearance can be observed prior to the time point assessed but must be observed at the given week of interest.

5.4.1.1.4.1. On Treatment

HBsAg seroclearance will be evaluated over time during the study intervention phase.

5.4.1.1.4.2. Off Treatment

HBsAg seroclearance will be evaluated over time at each of the FU timepoints separately, with emphasis at 12, 24, 36 and 48 weeks after stopping all study interventions at the end of treatment period 2 and without restarting NA treatment.

HBsAg seroclearance will be also evaluated when assessed at 12, 24, 36 and 48 weeks after stopping all study interventions (regardless when intervention was stopped) and without restarting NA treatment.

For the analyses of seroclearance at the time points mentioned above, participants with HBsAg seroclearance at the respective time points (and without restarting NA treatment during the interval between the time of stopping the study intervention up to the analysis time point (FU Week 12, 24, 36 and 48)) will be considered as having achieved this endpoint.

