5.4.1.1.11. Suppressed HBV DNA

HBV DNA < LLOQ (HBV DNA detectable or HBV DNA TND) will be evaluated over all time points when assessed with emphasis at FU Weeks 12, 24, 34 and 48, after stopping all study interventions at the end of treatment period 2 and without restarting NA treatment.

HBV DNA < LLOQ (HBV DNA detectable or HBV DNA TND) will also be evaluated at 12, 24, 36 and 48 weeks after stopping all study interventions (regardless when intervention was stopped) and without restarting NA treatment.

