5.4.1.1.14. Partial Cure

Partial cure will be evaluated at each of the following time points separately: FU Week 12, 24, 36 and 48. A participant will be defined as having achieved partial cure if he/she has:

- Stopped all study interventions at any time, and
- had HBV DNA level $< 2,000$ IU/ml at the given week of interest, and
- had HBsAg $\geq LLOQ$ at the given week of interest, and
- not required NA re-treatment after stopping all study interventions.

Of note, HBV DNA level $< 2,000$ IU/ml may be achieved prior to the week of interest but must be observed at the given week of interest.

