5.4.2.1.3. HBsAg Seroclearance

5.4.2.1.3.1. On Treatment

The count and proportion of participants (and associated 90% CI) who achieve HBsAg seroclearance over time during the study intervention phase will be summarized.

5.4.2.1.3.2. Off Treatment

The count and proportion of participants (and associated 90% CI) who achieve HBsAg seroclearance over time during FU will be summarized. Separate analyses will be performed for participants who completed treatment as planned (at the end of treatment period 2), and regardless when treatment was stopped.

The count and proportion of participants who achieve HBsAg seroclearance will be evaluated at each of the following off-treatment time points: 12, 24, 36 and 48 weeks, respectively, after stopping all study interventions and without restarting NA treatment. In an additional summary, these proportions will be calculated with the denominator including only those participants who have reached the off-treatment timepoint (week 12, 24, 36 or 48), and have stopped all interventions including NA and have not restarted NA prior to the timepoint of interest.

For all time points, HBsAg seroclearance will be analyzed using the observed case data. LOCF will be used for selected time points (Section 5.4.2.1.1).

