5.5.1.4. Endpoints for Correlation

5.5.1.4.1. Association Between Baseline Characteristics/Viral Blood Markers and Selected Efficacy Variables

Correlations between baseline characteristics and on-treatment HBV blood markers with off-treatment endpoints will be evaluated. The list of HBV blood markers, including but not limited to, are defined in [Table 6](#).

A categorical off-treatment HBV marker will be evaluated if there is at least 10% response.

Table 6: Pairs of off treatment endpoints and baseline characteristics/on treatment HBV markers

Off treatment HBV marker	Baseline Characteristics/On treatment HBV marker
HBsAg change from baseline at FU Week 24	
 • Age • HBsAg value at baseline • HBsAg change from baseline at Week 12 • HBsAg change from baseline at Week 24 • NA treatment completion at Week 24 (Yes; No) • Treatment failure (Yes; No)
HBsAg change from baseline at FU Week 48	
 • Age • HBsAg value at baseline • HBsAg change from baseline at Week 12 • HBsAg change from baseline at Week 24 • NA treatment completion at Week 24 (Yes; No) • Treatment failure (Yes; No)
HBsAg seroclearance at FU Week 24 (Yes; No)	
 • Age • HBsAg value at baseline • HBsAg change from baseline at Week 12 • HBsAg change from baseline at Week 24 • NA treatment completion at Week 24 (Yes; No) • Treatment failure (Yes; No)
HBsAg seroclearance at FU Week 48 (Yes; No)	
 • Age • HBsAg value at baseline • HBsAg change from baseline at Week 12 • HBsAg change from baseline at Week 24 • NA treatment completion at Week 24 (Yes; No) • Treatment failure (Yes; No)
NA re-treatment at FU Week 24 (Yes; No)	
 • Age • HBsAg value at baseline • HBsAg change from baseline at Week 12 • HBsAg change from baseline at Week 24 • Treatment failure (Yes; No)
NA re-treatment at FU Week 48 (Yes; No)	
 • Age • HBsAg value at baseline • HBsAg change from baseline at Week 12 • HBsAg change from baseline at Week 24 • Treatment failure (Yes; No)
Partial cure at FU Week 24 (Yes; No)	
 • Age • HBsAg value at baseline

Table 6: Pairs of off treatment endpoints and baseline characteristics/on treatment HBV markers

Off treatment HBV marker	Baseline Characteristics/On treatment HBV marker

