	
 • HBsAg change from baseline at Week 12 • HBsAg change from baseline at Week 24 • Treatment failure (Yes; No)
Partial cure at FU Week 48 (Yes; No)	
 • Age • HBsAg value at baseline • HBsAg change from baseline at Week 12 • HBsAg change from baseline at Week 24 • Treatment failure (Yes; No)
Functional cure at FU Week 24 (Yes; No)	
 • Age • HBsAg value at baseline • HBsAg change from baseline at Week 12 • HBsAg change from baseline at Week 24 • NA treatment completion at Week 24 (Yes; No) • Treatment failure (Yes; No)
Functional cure at FU Week 48 (Yes; No)	
 • Age • HBsAg value at baseline • HBsAg change from baseline at Week 12 • HBsAg change from baseline at Week 24 • NA treatment completion at Week 24 (Yes; No) • Treatment failure (Yes; No)

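### SAP functional cure tests whether the NA stopping criteria were met at Week 24, not whether NA was stopped, so a participant still taking NA can be counted

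*SAP*

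**What the plan says.** SAP 5.4.1.1.5 evaluates functional cure at FU Weeks 12, 24, 36 and 48. Its first condition reads "met the criteria for stopping NA treatment at Week 24, and". The second is HBsAg seroclearance at the week in question, which SAP 5.4.1.1.4 defines as a quantitative value below LLOQ (0.05 IU/mL). The third is that the participant has "not required NA re-treatment between FU Week 2 and the given week of interest".

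SAP 5.4.1.1.1 defines the stopping criteria as HBsAg <10 IU/mL, HBeAg-negative, HBV DNA <LLOQ and ALT <3x ULN, all assessed from laboratory tests. The analysis section, SAP 5.4.2.1.4, adds rules for missing data but no condition on NA use.

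The neighbouring endpoints are written differently. Partial cure (SAP 5.4.1.1.14) opens with "Stopped all study interventions at any time, and". One form of off-treatment seroclearance (SAP 5.4.1.1.4.2) is assessed after "stopping all study interventions (regardless when intervention was stopped) and without restarting NA treatment". Suppressed HBV DNA (SAP 5.4.1.1.11) is assessed "after stopping all study interventions at the end of treatment period 2 and without restarting NA treatment". An additional seroclearance summary (SAP 5.4.2.1.3.2) restricts its denominator to those who "have stopped all interventions including NA and have not restarted NA prior to the timepoint of interest".

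SAP Table 6, titled "Pairs of off treatment endpoints and baseline characteristics/on treatment HBV markers", lists functional cure at FU Weeks 24 and 48 among the off-treatment markers. Protocol 2.1 also places functional cure under off-treatment efficacy.

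**The concern.** Loss of HBsAg while NA continues is a different finding from loss of HBsAg that holds without treatment. Functional cure is reported and correlated as the second kind. As written, its conditions can be satisfied by someone who is still on NA, or back on it, so the two findings can be mixed in one count. The definition of functional cure is also looser about being off NA than the definition of partial cure.

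The third condition has a related gap. The SAP does not define 'required'. SAP 5.4.1.1.2 takes 'met the re-treatment criteria' and 'actually re-started NA' from two separate CRF pages, and SAP 5.4.2.1.2.1 cross-tabulates them because they can differ. Protocol 6.7.1 allows the investigator to restart NA before any cut-off is reached.

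**Working it through.** **Step 1. Compare the definitions.**

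| SAP endpoint | Must NA have been stopped? | Condition on returning to NA |
|---|---|---|
| Functional cure (5.4.1.1.5) | Not stated; Week 24 laboratory criteria only | Re-treatment not 'required' (undefined) |
| Partial cure (5.4.1.1.14) | Yes | Re-treatment not 'required' (undefined) |
| Off-treatment HBsAg seroclearance (5.4.1.1.4.2) | Yes | NA not restarted |
| Off-treatment HBV DNA <LLOQ (5.4.1.1.11) | Yes | NA not restarted |

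SAP 5.1 includes NA in each study intervention, and SAP 5.4.1.1.16 says that off-treatment means after stopping all of them, NA included. The lower three rows are therefore true off-NA conditions.

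**Step 2. Does 'criteria met' imply 'NA stopped'?** Usually. Protocol 6.6 and footnote uu of the Schedule of Activities stop NA at FU Week 2 when the criteria are met at Week 24. The link is not complete:

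- Protocol 6.6 and 7.1 allow a participant who discontinues investigational treatment early to continue NA.
- Protocol 8.3.6.6 says NA should be continued when JNJ-3989 (and PegIFN-α2a) is discontinued for confirmed grade 3 or 4 hematologic abnormalities.
- These participants enter follow-up unless they withdraw consent. SAP Table 3 runs Treatment Period 2 to at least the projected or actual Week 24 date for those still in the study, so they can have laboratory values in the Week 24 window (days 156-183).
- A departure from the FU Week 2 stop leads to the same place.

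**Step 3. Apply the rule to hypothetical participants.**

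- *A* discontinues JNJ-3989 and PegIFN-α2a in Treatment Period 2, continues NA as the protocol allows, meets all four criteria at Week 24, and has HBsAg <0.05 IU/mL at FU Week 24. Conditions 1 and 2 hold. Condition 3 holds trivially, because NA never stopped. A counts as functionally cured, but not as off-treatment seroclearance.
- *B* stops NA at FU Week 2, is restarted early at the investigator's discretion, never meets the re-treatment criteria, and has HBsAg <LLOQ at the week of interest. B counts if 'required' means 'criteria met', and does not count if it means 'restarted'.

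**Step 4. Scale.** The SAP uses the two-sided 90% Clopper-Pearson interval: lower limit = Beta quantile 0.05 with parameters (x, n-x+1); upper limit = Beta quantile 0.95 with parameters (x+1, n-x). For x=25, n=50 this gives 0.376-0.624, width 0.248, which agrees with SAP Table 1. The same formula at n=50 gives:

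| x/n | Proportion | 90% CI |
|---|---|---|
| 0/50 | 0% | 0-5.8% |
| 1/50 | 2.0% | 0.1-9.1% |
| 4/50 | 8.0% | 2.8-17.4% |
| 5/50 | 10.0% | 4.0-19.9% |

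The main analysis uses observed cases, so the denominator may be smaller. One participant is worth 1/50 = 2.0 points, 1/40 = 2.5 points or 1/30 = 3.3 points (40 and 30 are assumptions).

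SAP 5.5.1.4.1 evaluates a categorical marker in Table 6 only if at least 10% respond. One participant can decide that: 4/50 = 8.0% is not evaluated and 5/50 = 10.0% is. These counts were chosen to straddle the threshold; nothing in the documents predicts them.

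**The case against.** The strongest reply is that the SAP is to be read with the protocol, and the protocol requires NA to stop at FU Week 2 once the criteria are met. The third condition starts its clock at that visit and speaks of re-treatment, which presupposes a stop. Read together, the definition is aimed at people who came off NA, and an early discontinuer would still have to meet all four Week 24 criteria and later have HBsAg <0.05 IU/mL. This establishes the intent and shows that few participants can be affected. It does not close the gap, because the protocol itself provides for some early discontinuers to remain on NA, and a derivation programmed from the three conditions would not exclude them.

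It is also fair to say that a participant restarted on NA has, in ordinary language, required it. But the SAP records meeting the criteria and restarting as separate facts and does not say which one the condition uses.

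Functional cure is absent from the objectives and endpoints tables in both documents, the study tests no formal hypothesis, and correctly worded off-treatment seroclearance is tabulated at the same four time points. All of that stands, and it limits the consequence. Those tables and the follow-up NA exposure summary could reveal a mismatch, but they would not correct the functional-cure count.

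**Conclusion.** The definition omits a condition that its intended meaning needs. This is a wrong rule in a descriptive endpoint, not merely missing detail. It can admit participants who stayed on NA after meeting the Week 24 criteria and, on one reading of 'required', participants restarted early.

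Three stronger conclusions might be inferred, and the documents support none of them:

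- *That the reported functional-cure rate will be inflated.* The documents do not show that any participant falls into either group, and the number cannot be derived. The 2-point shift at n=50 is the value of one such participant, not an estimate of bias.
- *That the main efficacy results are affected.* The primary endpoint is the Week 24 HBsAg decline. The listed Week 48 seroclearance endpoint is tied to completing all study interventions and not restarting NA. Neither uses this definition.
- *That meeting the re-treatment criteria should itself count as failure.* Protocol 4.2 notes that ALT elevations after stopping NA may reflect immune activation and can lead to functional cure. A participant who met the criteria during a flare, stayed off NA and then cleared HBsAg is the kind of response sought.

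The conclusion assumes that functional cure is meant as an off-treatment result, as SAP Table 6 and protocol 2.1 indicate.

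**What to change.** In SAP 5.4.1.1.5, keep the condition that the NA stopping criteria were met at Week 24 and keep HBsAg seroclearance at the week of interest. Replace the third condition with: *stopped all study interventions including NA by the FU Week 2 visit, and received no NA from then up to the given week of interest (per the Study Drug Administration for NA CRF page)*.

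The date matters. A bare requirement to have stopped NA would admit someone who stopped shortly before the assessment. Do not add meeting the re-treatment criteria as a failure condition. Partial cure already requires stopping and can otherwise stay as it is.

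The cost is a short change to the SAP text and its derivation. The CRF page is already named in SAP 5.4.1.1.2, so no new data or visits are needed. The downside is that a few participants, including any who stopped NA after FU Week 2, may no longer count as responders.

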2.3.1.2. Potential Benefits

Results from clinical studies with JNJ-3989, JNJ-6379, NAs, and PegIFN- α 2a may be useful for the development of a novel therapeutic approach for chronic HBV infection.

The combination of JNJ-6379 and JNJ-3989 on a background of NAs would target different stages of the viral life cycle. While NA treatment reduces HBV DNA to levels close to or below the LLOQ of the HBV DNA assay, HBV replication is not completely inhibited, resulting in replenishment of the cccDNA pool. The addition of JNJ-6379, which targets the HBV capsid assembly (“primary” mode of action [MoA]) and the de novo cccDNA formation (“secondary” MoA), is expected to block HBV replication more profoundly by inhibiting formation of HBV RNA and DNA containing particles, and to inhibit de novo cccDNA formation, ultimately leading to reduction in cccDNA levels/transcriptional activity and HBsAg seroclearance (“intensified viral suppression”). The addition of JNJ-3989 is expected to intensify viral suppression by downregulating levels of the HBV DNA precursor pgRNA. In addition, JNJ-3989 reduces levels of all viral proteins including HBsAg, which is known to interfere with the host immune responses (Fang 2015; Li 2018; Wang 2013). By acting on both viral replication and by reducing barriers to the host immune-responses, higher functional cure rates may be achieved.

The addition of short-term PegIFN- α 2a (12 weeks) to the regimen may lead to further improvement of the immune response (such as reactivation of NK-cells) and ultimately could lead to immune control of HBV (ie, functional cure). In addition, PegIFN- α 2a has shown to have direct antiviral effects on HBV which could also contribute to the efficacy of the regimen. By adding short-term PegIFN- α 2a to the regimen, higher functional cure rates may be achieved.

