Furthermore, the sponsor decided to make additional changes to the study design because of a severe clinical ALT flare that was reported following discontinuation of NA treatment in a participant who was randomized to the control arm (placebo + placebo + NA) in the REEF-2 study. Discontinuation of NA treatment was following the protocol-defined criteria and in line with recent EASL treatment guidelines (EASL 2017). Flares following NA discontinuation are not unexpected, but the rapid evolution and clinical deterioration seen in this participant who had no history or evidence of liver cirrhosis was unforeseeable. Therefore, to protect the safety of participants, the protocol was amended: more frequent monitoring of participants who discontinued NA treatment during follow-up was included and the NA re-treatment criteria for all participants who discontinued NA treatment were revised.

Criteria for Completion of NA Treatment

At the end of Treatment Period 2 (Week 24/EOSI), all participants will enter the FU Period and stop treatment with JNJ-3989 and PegIFN- α 2a. If the protocol-defined NA treatment completion criteria (described in Section 6.6, Study Intervention Completion at Week 24) have been met at Week 24, NA will also be stopped at the next scheduled visit (ie, at FU Week 2), otherwise NA treatment will continue during the complete FU duration. The NA treatment completion criteria which take ALT, HBV DNA, HBeAg, and HBsAg levels into consideration, have been selected to ensure that only participants with a chance of sustained off-treatment response are allowed to stop all study intervention. Across a range of studies, HBsAg levels below 100 IU/mL are consistently associated with favorable off-treatment response (Jeng 2018; Papatheodoridis 2018). The stringent HBsAg cut-off of 10 IU/mL for NA treatment completion was chosen to account for the direct effect of JNJ-3989 on HBsAg levels.

After stopping all study interventions, participants will be monitored closely during the 48-week FU Period and should re-start NA treatment in accordance with the NA re-treatment criteria (see Section 6.7.1, NA Re-treatment Criteria and Monitoring After Stopping of NA, for more details).

Follow-up Procedures and Criteria for Re-initiation of NA Treatment

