4.3.1. JNJ-3989

Clinical data on PK and safety of JNJ-3989 are available from the Phase 1/2a AROHBV1001 study with a data cut-off date of 29 October 2019. In addition, snapshot efficacy and PD data are available with a data cut-off date of 26 March 2020. The study has been completed and final analysis and report writing are ongoing. Twenty adult healthy participants have received single subcutaneous injections of JNJ-3989 (35, 100, 200, 300, and 400 mg) and 84 adult chronic HBV-infected participants have received multiple doses of JNJ-3989 (25, 50, 100, 200, 300, and 400 mg), administered as 3 subcutaneous injections separated by either 7-day, 14-day, or 28-day intervals. All participants either continued or started on ETV or tenofovir disoproxil on Day 1.

JNJ-3989 was generally safe and well tolerated at all doses. No clinically relevant safety signal was identified.

Antiviral activity data were available for 56 chronic HBV-infected participants who received 3 subcutaneous injections of 25 to 400 mg JNJ-3989 Q4W (Gane 2019; Yuen 2019; IB JNJ-3989 2020). In general, mean HBsAg declines reached nadir at Day 113 (ie, 8 weeks after last JNJ-3989). Mean HBsAg levels remained suppressed (below baseline levels) at least until Day 392 (ie, 9 months after last dose) in a substantial proportion of patients. The HBsAg levels at Day 392 were variable with some patients having HBsAg levels close to baseline levels while a substantial proportion of patients still had HBsAg levels $>1 \log_{10}$ IU/mL lower than the baseline levels. JNJ-3989 showed activity on other viral markers (HBV DNA, HBV RNA, HBeAg and HBcrAg), frequently with sustained reduction at least until Day 362. No apparent dose response was observed

at doses between 100 mg and 400 mg JNJ-3989, a numerically smaller mean decline was observed at the lower doses of 25 mg and 50 mg, mainly apparent after end of JNJ-3989 dosing.

A dose of 200 mg JNJ-3989 Q4W is chosen based on the observed decline in HBsAg in Study AROHBV1001 at this dose over 3 injections, and the lack of a substantial incremental efficacy response at higher doses.

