6.7.1. NA Re-treatment Criteria and Monitoring After Stopping of NA

Participants who meet the protocol-defined NA treatment completion criteria outlined in Section 6.6, Study Intervention Completion at Week 24, will be monitored closely during the FU Period.

After stopping NA treatment, participants should be monitored as follows:

- Regular monitoring visits will be every 4 weeks during the follow-up phase in accordance with the [Schedule of Activities](#).
- A post-treatment HBV DNA value of >20,000 IU/mL should trigger re-testing of ALT/AST, HBV DNA, and total and direct bilirubin within a maximum of 7 days from receipt of the data and further repeats as necessary (ie, weekly until HBV DNA returns to <20,000 IU/mL).
- A post-treatment HBV DNA value of >2,000 IU/mL (but <20,000 IU/mL) should trigger a re-test within 14 days from receipt of the data and further repeats as necessary (ie, every other week until HBV DNA returns to <2,000 IU/mL).
- A post-treatment ALT value of >5x ULN should trigger re-testing of ALT, AST, ALP, total and direct bilirubin, INR, albumin, and HBV DNA on a weekly basis until ALT and AST levels have returned to <5x ULN.

After stopping NA treatment, participants should re-start NA treatment:

- Immediately with signs of decreasing liver function based on laboratory findings (eg, INR, direct bilirubin) or clinical assessment (eg, ascites, hepatic encephalopathy).
- Immediately with an HBV DNA value of >100,000 IU/mL (irrespective of confirmation and/or ALT increase).
- With confirmed post-treatment HBeAg seroreversion (HBeAg positive after it was negative at NA completion).
- With confirmed* post-treatment increases in HBV DNA >2,000 IU/mL and ALT >5x ULN.

- With confirmed* post-treatment increases in HBV DNA >20,000 IU/mL.

* *At least 4 weeks apart – frequency of visits as described above*

Note: Additional re-testing and/or earlier restarting of NA treatment is at the investigator's discretion, even if the above cut-offs are not yet met.

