5.4.1. Definitions

5.4.1.1. Binary Endpoints

5.4.1.1.1. NA Treatment Completion Criteria at Week 24 and During FU

NA treatment completion criteria are defined based on laboratory results at Week 24 as follows:

- HBsAg <10 IU/mL, and
- HBeAg-negative, and
- HBV DNA <LLOQ, and
- ALT <3x ULN

The NA completion criteria will be assessed based on clinical laboratory tests and summarized at Week 24 (EOSI) and during FU phase.

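### Functional cure applies no HBV DNA test at the follow-up week where it is scored, so sustained viraemia up to about 20,000 IU/mL can count as cure

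*SAP*

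**What the plan says.** SAP 5.4.1.1.5 sets three conditions for functional cure at FU Week 12, 24, 36 or 48:

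1. "met the criteria for stopping NA treatment at Week 24, and"
2. "had HBsAg seroclearance at the given week of interest, and"
3. no NA re-treatment required from FU Week 2 up to that week.

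Condition 1 points to SAP 5.4.1.1.1, which includes "HBV DNA <LLOQ, and" but takes the value at Week 24. Participants who meet those criteria stop NA afterwards, at FU Week 2 (Protocol 6.6).

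Condition 3 depends on Protocol 6.7.1. Its HBV DNA and ALT triggers are a single HBV DNA value above 100,000 IU/mL; "With confirmed* post-treatment increases in HBV DNA >20,000 IU/mL", with confirmation at least 4 weeks apart; or confirmed HBV DNA above 2,000 IU/mL together with ALT above 5x ULN. Signs of decreasing liver function and confirmed HBeAg seroreversion also trigger a restart, and the investigator may restart earlier.

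Two other SAP definitions do test HBV DNA off treatment. A confirmed virologic flare is two consecutive values above 200 IU/mL in a participant who was below LLOQ at the last point on all study treatments (5.4.1.1.16). Partial cure requires "had HBV DNA level $< 2,000$ IU/ml at the given week of interest, and", and also HBsAg at or above LLOQ (5.4.1.1.14).

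The protocol does not define functional cure. Section 2.3.1.2 equates it with immune control of HBV.

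**The concern.** The Week 24 HBV DNA value is taken on NA, so it says nothing about viral control once NA has stopped. After that, functional cure limits HBV DNA only through the safety triggers for restarting NA. Those triggers were written to protect participants, not to define a response, and they leave a wide range of replication open.

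Protocol 2.1 says off-treatment efficacy will be explored to see whether the regimen can induce functional cure. A rate that may include participants with ongoing replication does not answer that question cleanly. Any misclassification also carries into the by-response summaries (SAP 5.4.2.2.1) and the correlations with functional cure at FU Weeks 24 and 48 (SAP Table 6).

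As written, the endpoint also adds little to off-treatment HBsAg seroclearance without NA restart, which SAP 5.4.1.1.4.2 already evaluates at the same four weeks. The main addition is the set of Week 24 stopping criteria, which normally decide who stops NA anyway.

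**Working it through.** **Inputs.** HBsAg LLOQ 0.05 IU/mL and HBV DNA LLOQ 20 IU/mL (SAP Table 5); re-treatment triggers (Protocol 6.7.1); flare threshold 200 IU/mL (SAP 5.4.1.1.16); partial cure HBV DNA limit 2,000 IU/mL (SAP 5.4.1.1.14).

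**Definitions side by side.** Take a participant who met the Week 24 criteria, has HBsAg <0.05 IU/mL at the scoring week, and has no liver-function sign, HBeAg seroreversion or discretionary restart.

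| HBV DNA (IU/mL) | Re-treatment required on DNA/ALT? | Virologic flare if on two consecutive visits? | Under the 2,000 limit? | Functional cure? |
|---|---|---|---|---|
| <20 | No | No | Yes | Yes |
| 20 to 200 | No | No | Yes | Yes |
| >200 to <2,000 | No | Yes | Yes | Yes |
| 2,000 to 20,000, ALT ≤5x ULN | No | Yes | No | Yes |
| >2,000 with ALT >5x ULN, confirmed | Yes | Yes | No | No |
| >20,000 to 100,000, not yet confirmed | Not yet | Yes | No | Yes, until confirmed |
| >20,000, confirmed | Yes | Yes | No | No |
| >100,000, once | Yes | Yes | No | No |

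**Width of the gap.** log10(20,000/20) = 3.0 above LLOQ. The same ceiling is 20,000/200 = 100 times the flare threshold and 20,000/2,000 = 10 times the partial cure limit.

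**Example.** HBsAg <0.05 IU/mL, HBV DNA 15,000 IU/mL and ALT 4x ULN (and at least 3x nadir) at consecutive visits. The HBV DNA values make a confirmed virologic flare and the ALT values a biochemical flare. They overlap, so this is also a clinical flare (SAP 5.4.1.1.16). No HBV DNA or ALT trigger is met, so condition 3 holds and the participant is scored as functionally cured.

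**The word required.** SAP 5.4.1.1.2 uses two separate CRF pages, one for NA actually restarted and one for re-treatment criteria met, and 5.4.2.1.2.1 cross-tabulates them. Condition 3 does not say which applies. If it means restarted, a participant who met a trigger but did not restart stays a responder, and the 20,000 IU/mL ceiling weakens. If it means criteria met, a participant restarted early at the investigator's discretion could stay a responder while on NA.

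**Effect on the estimate.** The plan gives no figure for functional cure. Its interval method does reproduce: the exact 90% Clopper-Pearson interval for 25/50 is 0.376 to 0.624, width 0.248, as in SAP Table 1. Applied to small counts, assuming all 50 are evaluable:

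| Counted as cured | Rate | 90% CI |
|---|---|---|
| 0/50 | 0% | 0.000 to 0.058 |
| 1/50 | 2% | 0.001 to 0.091 |
| 2/50 | 4% | 0.007 to 0.121 |
| 3/50 | 6% | 0.017 to 0.148 |
| 5/50 | 10% | 0.040 to 0.199 |

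Each reclassified participant moves the estimate by 1/50 = 2 percentage points. If three were counted and one was viraemic, 6% would become 4%. The main analysis uses observed cases (SAP 5.4.2.1.4), so with fewer than 50 evaluable each participant weighs slightly more.

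**The case against.** **HBV DNA is not absent.** A reader might infer that functional cure carries no HBV DNA requirement at all, or that viraemia below 20,000 IU/mL can never lead to re-treatment. Neither is right. Condition 1 requires HBV DNA below LLOQ at Week 24, and the liver-function, HBeAg-seroreversion and discretionary routes to restart apply at any HBV DNA level. What remains is that nothing tests HBV DNA at the scoring week.

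**Partial cure is not a lower rung.** It is tempting to say the response hierarchy is inverted. The documents do not support that. Partial cure requires HBsAg at or above LLOQ, so the categories are disjoint, and the example participant fails partial cure on HBsAg whatever the HBV DNA value. The 2,000 IU/mL limit shows only that the SAP treats off-treatment HBV DNA as relevant to response elsewhere.

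**Residual drug is not shown to create false cures.** FU Weeks 12, 24, 36 and 48 are 16, 28, 40 and 52 weeks after the last JNJ-3989 dose at Week 20 (24 + FU week − 20). Protocol 4.2 says the 10 IU/mL stopping cut-off was "chosen to account for the direct effect of JNJ-3989 on HBsAg levels", and 4.3.1 reports: "Mean HBsAg levels remained suppressed (below baseline levels) at least until Day 392". But below baseline is not below LLOQ: from the entry minimum of 100 IU/mL, seroclearance needs a fall of more than log10(100/0.05) = 3.3. Protocol 2.2.1 and 2.2.3.1 also say JNJ-3989 lowers HBV DNA, so carry-over would not by itself give viraemia with HBsAg below LLOQ. An HBV DNA test would not cleanly separate carry-over from immune control either.

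**Much is reported elsewhere.** HBV DNA below LLOQ off treatment is summarised at the same four weeks (SAP 5.4.2.1.10), and virologic flares are graded. SAP 5.4.2.1.11 gives HBsAg and HBV DNA both below LLOQ, but only at the last available timepoint. Separate marginal proportions cannot show how many participants meet both at a given week.

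**The threshold is a choice.** No document fixes an HBV DNA limit for functional cure, and at LLOQ one low-level value would fail a participant. That stands. LLOQ is nevertheless the limit the plan already uses for its Week 48 secondary endpoint and its joint table.

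**Conclusion.** The gap in the definition is real. At the week functional cure is scored there is no HBV DNA test, and sustained values up to about 20,000 IU/mL, or an unconfirmed value up to 100,000 IU/mL, can count as cure. This assumes ALT not above 5x ULN, no other restart reason, and condition 3 read as criteria met.

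The practical size is unknown. The documents give no frequency for HBsAg below LLOQ with HBV DNA at or above LLOQ, and the combination may be rare. If it never occurs, the reported rate does not change. If cures are few, one or two such participants could be a visible share of them.

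The primary endpoint is unaffected, the study has no formal hypothesis, and functional cure is not listed in the objectives and endpoints table. This is an inexpensive improvement to an exploratory but closely watched outcome, not a flaw in the main result.

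**What to change.** - Add a fourth condition to SAP 5.4.1.1.5: HBV DNA below LLOQ, target detected or not, at the same FU week. In the sensitivity analyses of 5.4.2.1.4, handle missing HBV DNA as 5.4.2.1.13 does for partial cure. Keep the HBsAg-only result as the existing off-treatment seroclearance endpoint.
- At minimum, leave the definition and report the joint proportion of 5.4.2.1.11 (HBsAg and HBV DNA both below LLOQ) at each of FU Weeks 12, 24, 36 and 48, not only at the last available timepoint.
- In either case, state whether condition 3 means re-treatment criteria met or NA actually restarted, and name the CRF page used.

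The cost is SAP wording and some programming. The Schedule of Activities already samples HBV DNA at every follow-up visit, so no new data are needed. The reported functional cure rate may fall slightly, by 2 percentage points per reclassified participant of 50.
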